### 5.2.2 HIGHER UFNET RATES IN THE FIRST 48 HOURS OF CKRT ARE ASSOCIATED WITH MORTALITY

We also examined the association between the UFNET rate within the first 48-hours of use of CKRT and hospital mortality in an independent cohort of 347 critically ill patients. UFNET rates >1.75 mL/kg/h compared with rates <1.01 mL/kg/h (aHR range, 1.27-4.18, P=0.03) was associated with 28-day mortality. In a subsequent mediation analysis, we found that this higher risk of death was not mediated by fluid balance, blood pressure, vasopressors, or electrolytes, implying that higher UFNET rates may have a direct causal effect on the risk of death.

### 5.2.3 LOWER UFNET RATES ARE ALSO ASSOCIATED WITH MORTALITY IN PATIENTS WITH FLUID OVERLOAD

[figure not shown]
Using the UPMC ICU database of patients with >5% fluid overload and treated with CKRT and IHD (n=1,075), we evaluated the association of UFNET rate over 24-hour period and 1-year mortality. We found that the UFNET rates <20 mL/kg/day, compared with rates >25 mL/kg/day, were associated with increased risk-adjusted mortality. Of the CKRT subgroup, hourly UFNET rates <0.5 mL/kg/h compared with rates >1.0 mL/kg/h was also associated with death. These findings suggest that minimum UFNET rates of >20 mL/kg/day or >1.0 mL/kg/h using CKRT is associated with a lower risk of death among patients with fluid overload. Using Mayo Clinic data, UFNET rates <35 mL/kg/day compared with ≥35 mL/kg/day were also associated with the risk of major adverse kidney events. These studies suggest that a minimum rate of at least 1.0 mL/kg/h is associated with reduced mortality compared with slower rates.

### 5.2.4 BAYESIAN HETEROGENEITY IN TREATMENT EFFECT ASSOCIATED WITH THE UFNET RATE

Using cluster analysis in RENAL, the probability of harm associated with UFNET rates >1.75 mL/kg/h was 99.6% compared with UFNET rates of 1.01-1.75 mL/kg/h, and 32.5% compared with UFNET rates <1.01 mL/kg/h among the subgroup of severely ill patients who had sepsis,

metabolic acidosis, organ edema, those treated with mechanical ventilation and vasopressors (Figure 4). The probability of harm associated with  $UF_{NET}$  rates between 1.01-1.75 mL/kg/h compared with the rates <1.01 mL/kg/h was only 0.2%. Of patients who are hemodynamically unstable with cardiovascular sequential organ failure assessment (SOFA) score of 3 or more, both  $UF_{NET}$  rates >1.75 mL/kg/h and rates <1.01 mL/kg/h were associated with increased mortality compared with rates 1.01-1.75 mL/kg/h.

**Figure 4: Posterior probability of the  $UF_{NET}$  rate group treatment effect (log [HR]) in each cluster. The tables contain the probability that the hazard ratio for 90-day mortality in the high  $UF_{NET}$  group (plots A and B) is above 0 (i.e., a hazard ratio above 1, suggestive of harm).**

## 5.2.5 ADVERSE EVENTS FREQUENTLY OCCUR DURING CONTINUOUS DIALYSIS

[figure not shown]
In a cohort of 1,743 patients receiving continuous KRT at Mayo Clinic ICUs, intradialytic hypotension (IDH) occurred frequently. IDH was defined as MAP  $\leq$ 60 mmHg, SBP <90mmHg or a decline in SBP  $>$ 40mmHg from baseline, a positive fluid balance  $>$ 500mL or increased vasopressor requirement. Early IDH occurred in 1,124 patients (64.6%) and was independently associated with mortality (Odds Ratio, 1.56, 95% CI: 1.25–1.9). IDH within the first hour occurred in 43% of patients, and 81% of patients had new onset of cardiac arrhythmias. Sinus tachycardia was present in 51% and atrial fibrillation in 11% (Table 1).

In a multinational survey of ICU practitioners in 80 countries IDH was reported by 20% (range, 20%–38%) of practitioners. When IDH occurred, practitioners decreased the rate of fluid removal (70.3%; Figure 5); started or increased vasopressor dose (51.5%); completely stopped fluid removal (35.8%); and/or administered a fluid bolus (31.6%) for treatment. Thus, IDH and interventions for IDH are common during KRT. Using the Acute Renal Failure Trial Network cohort, we found that IDH events occurred in 43.2% of patients. Of all hypotensive complications, hypotension requiring vasopressor use, discontinuation of KRT, and other interventions occurred in 13.2%, 8.4%, and 78.4%, respectively.

**Table 1: Incidence of adverse events during continuous KRT**

Parameter	No. (%)
Hypotension	258 (43)
Sinus tachycardia	306 (51)
Atrial fibrillation	64 (11)
Atrial flutter	6 (1)
Ventricular tachycardia	14 (2)
Sinus bradycardia	43 (7)
Ventricular fibrillation	19 (3)
Asystole	20 (3)
Others	12 (2)
Cardiac arrest	28 (5)

**Figure 5: Reported interventions performed for intra-dialytic hypotension by critical care practitioners**

#### 5.2.6 MULTINATIONAL SURVEY OF ATTITUDES TOWARDS UFNET PRACTICES

In a survey of 80 countries, two-thirds of practitioners (71%, regional range, 55%-95.5%) reported using CKRT for volume management. In the U.S., the reported initial median UFNET rate prescription was 100 (IQR, 78-200) mL/h and the maximum rate was 285 (IQR, 200-341) mL/h for hemodynamically stable patients and 51 (IQR, 25-100) mL/h for hemodynamically unstable patients. For an average 80-kg patient, a UFNET volume of 285 mL/h would be equivalent to a rate of 3.56 mL/kg/h, and 341 mL/h would be equal to a rate of 4.26 mL/kg/h in hemodynamically stable patients. These data suggest that the UFNET rates used in the liberal group is within the range of clinical practice. More than 80% of critical care practitioners believed a protocol-based fluid removal would be useful.

#### 5.2.7 CLINICIAN EQUIPOISE TO ENROLL IN CLINICAL TRIAL

In our survey, we asked critical care practitioners about attitudes towards UFNET practice and equipoise to enroll patients in a clinical trial of protocol based UFNET. Across regions, most practitioners (90.0%, range, 84.5% – 91.7%) agreed that early UFNET would be beneficial and protocol (81.4%, range, 62.3% – 88.3%) outlining the rate, volume and duration of UFNET would be useful. Two-thirds of clinicians (78.3%, range, 72.7% – 83.7%) indicated that they would be agreeable to enroll patients in a clinical trial of protocol based UFNET.

## 5.2.8 FEASIBILITY OF ENROLLMENT

In 2019, 412 unique patients were admitted to UPMC Presbyterian hospital ICUs and received treatment with CKRT. This averages 34 patients per month, and thus, an average of 2 patients per month enrollment would be feasible. The average duration of treatment with CKRT was four days. At Mayo Clinic, approximately 15 patients per month were treated with CKRT across the 3 ICUs in 2020. Thus, enrolling 144 patients across six ICUs over 30 months is feasible.

## 5.2.9 PHYSICIAN EQUIPOISE TO ENROLL AT UPMC AND MAYO CLINIC

Both at the UPMC and the Mayo Clinic, fluid removal is co-managed by intensivists and nephrologists. Thus, we conducted an email survey of intensivists and nephrologists (n=43) at both clinical sites. An overwhelming number of physicians (n=41; 95%) were willing to enroll in this trial. Reasons for unwillingness included massive fluid overload with ongoing large infusions, refractory hypoxemia, inability to close the abdominal surgical wound due to edema, and the decision already made to remove fluid rapidly. Our study design already excludes such patients. We have also discussed the protocol with ICU directors, chiefs of nephrology, intensivists, and nephrologists, at the Mayo Clinic and at the UPMC, and they are willing to aid with screening and enrollment.

## 5.3 RESTRICTIVE UFNET RATE STRATEGY

### 5.3.1 POTENTIAL ADVANTAGES

There are several potential benefits to restrictive UFNET rate strategy. First, it will allow more time for vascular refill and will reduce blood pressure variability and hypotensive episodes as both intradialytic blood pressure variability and hypotensive episodes have been associated with ischemic organ injury and increased mortality. Second, by preventing hypotensive episodes, restrictive UFNET rate is likely to reduce the need for subsequent interventions such as completely stopping UFNET, fluid administration, starting or increasing the dose of new vasopressor. Both discontinuing UFNET and administering fluids will offset any potential benefit of UFNET and increase risk of fluid overload. Third, restrictive UFNET rates may preserve myocardial blood flow and prevent episodes of cardiac arrhythmias. Fourth, restrictive UFNET rate may reduce the workload and burden on nursing staff due to decreased number of interventions required to treat intradialytic hypotension.

### 5.3.2 POTENTIAL DISADVANTAGES

Restrictive UFNET rate strategy may theoretically be associated with longer tissue exposure to fluid overload and may increase time to achieving euvolemia. Prolonged exposure to fluid overload may impair kidney recovery, prolong the duration of kidney replacement therapy, or increase ventilator dependence. However, the risks of prolonged exposure to FO associated with restrictive UFNET rate strategy must be balanced against the risk of ischemic organ injury due to hypotensive episodes and blood pressure variability associated with faster and more liberal UFNET rates used in clinical practice.

## 5.4 LIBERAL UFNET RATE STRATEGY

### 5.4.1 POTENTIAL ADVANTAGES

Liberal UFNET rate based on hemodynamics may result in better and earlier volume control including achieving daily negative fluid balance and overall, less positive cumulative fluid balance as documented in observational studies. By varying UFNET across a range of UFNET rates, the liberal UFNET group affords more flexibility to clinicians for rapid fluid removal for treatment of fluid overload.

### 5.4.2 POTENTIAL DISADVANTAGES

Liberal UFNET rate strategy might be associated with rapid and unpredictable decline in intravascular volume. Intravascular hypovolemia in turn reduces cardiac preload. Decreases in preload is associated with lower cardiac output and hypotension. Moreover, faster and frequent titration of UFNET will increase the workload for the clinicians, poor compliance with closer monitoring of hemodynamics, and increase subsequent interventions for treatment of hypotensive episodes including bolus fluid administration thereby offsetting potential benefits of rapid fluid removal.

## 5.5 A TRIAL OF UFNET STRATEGY IS WARRANTED IN CRITICALLY ILL PATIENTS

There are several compelling reasons why trial of UFNET rate strategy should be conducted. First, the net risk-benefits of treatment of fluid overload and UFNET rate on clinical outcomes remains unclear as current observational studies have significant limitations. Thus, there is a critical need to determine the optimal process of care for patients undergoing UFNET. In the absence of such a knowledge, effective treatment of fluid overload and safe provision of UFNET among critically ill patients will be problematic.

Second, the current clinical practice of UFNET is highly variable in ICUs and is not evidenced-based. Generation of robust evidence will result in development and adoption of clinical practice guidelines and is likely to reduce variability in clinical practice.

Third, critically ill patients are a more vulnerable population sensitive to hemodynamic perturbations. For instance, studies show that more than 19% to 97% of patients on CKRT have episodes of sudden hypotension, and IDH is associated with mortality in critically ill patients. Thus, generation of robust evidence base is needed to ensure there is no harm associated with current clinical practice as the existing practice is to use liberal UFNET rates in patients with stable hemodynamics until hypotension occurs.

Fourth, more than two-thirds of critical care practitioners surveyed indicated that they have equipoise to enroll patients in a clinical trial of protocol-based UFNET strategy suggesting uncertainty as to the optimal approach to fluid removal in critically ill patients. Finally, several aggressive interventions in critically ill patients have not found to be associated with improved outcomes, and perhaps harmful, underpinning the principle of “less is more”. For instance, among patients with acute respiratory distress syndrome (ARDS) higher tidal

volume strategy was associated with increased risk of ventilator-induced lung injury and mortality than lower tidal volume ventilation. Thus, dialysis-associated organ injury due to faster rate of fluid removal needs further evaluation.

## 5.6 POTENTIAL PITFALLS OF THE PROPOSED STUDY DESIGN AND ALTERNATIVE TRIAL DESIGNS

### 5.6.1 POTENTIAL PITFALLS OF THE PROPOSED STUDY DESIGN

#### 5.6.1.1 *Why use Predicted Body Weight for Dosing UFNET?*

In this protocol, we propose to use predicted body weight (PBW) for setting UFNET rate in both treatment groups. PBW will be estimated using a gender-specific calculator ([Appendix A](#)) based on measurement of patient's height by research staff at the time of study enrollment. We chose PBW for the following reasons: (i.) PBW has been used in several NIH sponsored ICU trials, (ii.) shown closely to approximate with IBW in males and females, (iii.) free of confounding by FO and catabolism due to critical illness, and other measurement errors by nursing staff, (iv.) could be precisely determined at study enrollment from patient height accurately measured by trained research staff.

We chose not to use measured body weight (MBW) and actual body weight for the following reasons. First, precise premorbid MBW is unknown in most critically ill patients. Weight documented in EMR during prior hospitalization cannot be used as a surrogate for premorbid weight because of confounding by underlying illness. Second, index hospital admission weight is likely to be confounded by the underlying condition that led to hospitalization (e.g., dehydration from sepsis may result in underestimation, and fluid overload from underlying worsening congestive heart may result in overestimation of MBW). Third, retrospective collection of hospital and ICU admission weights are prone to measurement errors and also confounded by daily fluid intake and output which are inaccurately documented on hospital wards. Fourth, following initiation UFNET, the patient MBW is likely to fluctuate widely with decreasing weight overtime due to UFNET and due to catabolic nature of many ICU illness.

#### 5.6.1.2 *Why not use both IHD and CKRT for UFNET instead of only CKRT?*

We chose CKRT for this feasibility trial instead of IHD for the following reasons: (i.) our survey revealed that more than 70% of respondents indicated using CKRT for volume management in the ICU, (ii.) evidence suggests that CKRT is superior to IHD for volume control in critically ill patients due to continuous nature of ultrafiltration over a 24-hour period in patients with severe fluid overload, (iii.) the UFNET rates used during IHD would be very different to that of UFNET rates used during CKRT thus confounding the effect of UFNET rates while on CKRT, on clinical outcomes, iv.) the optimal ultrafiltration rates in critically ill patients with AKI treated with CKRT is uncertain; and v.) CKRT is the predominant modality used for volume management at the UPMC and the Mayo Clinic ICUs.

## 5.6.2 ALTERNATIVE STUDY DESIGNS

We considered several alternative study designs in addition to the proposed study design (Table 2).

**Table 2: Strengths and Weaknesses of Alternative Study Designs**

Intervention	Control	Strengths	Weakness
<0.5 mL/kg/h	>1.75 mL/kg/h	
 
Less episodes of hemodynamic instability in the intervention arm
 
More flexibility in dosing in the control arm
 
	
 
May not be feasible to randomize to a rate <0.5 mL/kg/h as most clinicians would consider UFNET rate <0.5 mL/kg/h is clinically insignificant volume removal.
 
Exposure to wide UFNET rate ranges in the control arm.
 
May increase risk of hemodynamic instability in the control arm
 

0.5 – 1.0 mL/kg/h	1.7 – 2.2 mL/kg/h	
 
More flexibility in the slower arm
 
Less episodes of hemodynamic instability in the intervention arm
 
	
 
Too narrow range in the control arm and does not represent current clinical care.
 
Most clinicians would consider UFNET rate <1.0 mL/kg/h is clinically insignificant volume removal.
 

1.0 mL/kg/h	Clinicians determine the UF NET rate	
 
Mirrors clinical practice in the control arm
 
	
 
Variability among clinicians in titrating UFNET
 
May not have adequate separation between the two treatment arms to detect meaningful difference.
 

1.0 – 1.7 mL/kg/h	>2.0 mL/kg/h	
 
Observational studies suggest lower mortality in the intervention arm
 
	
 
Exposure to wide UFNET rate ranges in the control arm
 

UF NET rate guided by continuous monitoring of intravascular volume status (e.g., pulse pressure variation, stroke volume variation)	UF NET rate guided by traditional hemodynamic monitoring ( i.e. , heart rate, MAP)	
 
Precision UFNET rate guided by intravascular volume assessment
 
May reduce episodes of hemodynamic instability
 
	
 
Functional hemodynamic monitoring has only been validated for fluid administration but not fluid removal
 
Most clinicians do not use functional hemodynamic monitoring for fluid removal
 
Requires patient to be on a controlled mode of ventilation with no spontaneous respiratory effort to accurately assess pulse pressure and stroke volume variation.
 

## 5.7 OBJECTIVES

### Primary Objective

The primary objective of this randomized trial is to assess the feasibility of maintaining patients in restrictive and liberal UFNET rates, adherence to the protocol, and assess recruitment rate in preparation for a large multicenter randomized clinical trial.

## 5.8 END POINTS

### 5.8.1 PRIMARY OUTCOME

The three primary feasibility outcomes are as follows:

1. *The between-group difference in mean delivered UFNET rate*: The primary objective is to measure a minimum of 0.53 mL/kg/h separation in the delivered patient mean UFNET rates between the restrictive and liberal UFNET rate groups. We chose between-group separation as a feasibility metric because it is a robust measure of adherence to complex protocols and has been used in ICU trials assessing the feasibility of frequently titrated interventions. Specifically, we reasoned that a larger study would not be feasible if the separation in the UFNET rates were less than 0.5 mL/kg/h. We chose 0.5 mL/kg/h as a clinically meaningful difference because our preliminary data indicated that a 0.50 mL/kg/h increase in UFNET rate is associated with increased mortality.
2. *Protocol adherence*: Adherence assessed by protocol deviation varies as the function of the definition of deviation and the frequency of measurements. Thus, in this trial, we will define protocol deviation *a priori* as delivered UFNET rate that lies >0.5 mL/kg/h outside of the target UFNET rate range in the assigned treatment group for greater than six consecutive hours during fluid removal *without* significant changes in MAP (*i.e.*, MAP <65 mmHg or  $\geq$ 90 mmHg). As such, out of range UFNET rates >0.5 mL/kg/h beyond the target UFNET rate range in the assigned treatment group will not constitute a protocol deviation when the bedside team titrated the UFNET rate as required to manage the patient hemodynamics (*i.e.*, when clinicians appropriately decreased rate or stopped fluid removal for hypotension; increased rate for hypertension or for treatment of respiratory distress due to fluid overload and pulmonary edema).

We chose the above metric for protocol deviation because with complex interventions, as the frequency of monitoring increases, so does the resources required to track protocol adherence. Close monitoring of protocol deviations is unlikely in trials that lack resources, introducing a risk of ascertainment bias. In contrast, with very frequent monitoring of continuous interventions, the likelihood of recording protocol deviations increases but the clinical impact of each deviation diminishes proportionately. Similarly, criteria for protocol deviations that are too sensitive would exaggerate the impact of protocol deviations beyond what is clinically important and unduly undermine the apparent feasibility and internal validity of the trial.

All reasons for non-adherence will be recorded for both groups using pretested taxonomy distinguishing clinical reasons (*e.g.*, hypotension, hypertension, difficulty in oxygenation, respiratory distress, hemodynamic instability, attending override of protocol) and research-related reasons (*e.g.*, consent withdrawal).

3. *Recruitment rate*: A successful recruitment rate will be defined as achieving an enrollment rate of 1 patient per ICU per time window during the trial. While this feasibility trial is ongoing, recruitment will be reviewed weekly; the screening records

will be reviewed monthly, and the numbers of missed eligible patients will be investigated. If applicable, we will discuss barriers to enrollment and use well-developed strategies to improve recruitment. Therefore, recruitment will be maximized as necessary over the course of the trial. The recruitment metric will be measured and interpreted at the end of the trial by calculating the mean number (standard deviation) of recruited patients per active screening month.

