#### 8.3.2 REFERENCE MEASUREMENTS

The following data will provide the basis for assessing protocol compliance and safety as well as between-group differences. Data for each of the variables will be recorded on the days shown in the Time-Events schedule ([Appendix F](#)) until death, discharge from the ICU, or day 28, whichever occurs first. Values will be derived from clinically available data.

1.  $UF_{NET}$  rate
  - a. Restrictive  $UF_{NET}$  rate group
    - i. Time and initial  $UF_{NET}$  rate
    - ii. Time and target  $UF_{NET}$  rate
    - iii. Time and hourly  $UF_{NET}$  rate

- iv. Reason and duration of UFNET hold (if any)
- v. Total volume of UFNET during the study
- vi. Rescue UFNET (YES/NO)
  
- b. Liberal UFNET rate group
  - i. Time and initial UFNET rate
  - ii. Time and target UFNET rate
  - iii. Time and hourly UFNET rate
  - iv. Reason and duration of UFNET hold (if any)
  - v. Total volume of UFNET during the study
  - vi. Rescue UFNET (YES/NO)

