## 10 DATA COLLECTION AND SITE MONITORING

### 10.1 DATA COLLECTION

At the UPMC and the Mayo Clinic, the research staff will collect data and record it either on paper data sheets and/or enter in a secure web database. Once daily, coordinators will enter data that can be analyzed for consistency.

In this trial, we will define protocol deviation as delivered  $UF_{NET}$  rate that lies  $>0.5$  mL/kg/h outside of the target  $UF_{NET}$  rate range in the assigned treatment group for greater than six consecutive hours during fluid removal *without* significant changes in MAP (*i.e.*, MAP  $<65$  mmHg or  $\geq 90$  mmHg). As such, out of range,  $UF_{NET}$  rates  $>0.5$  mL/kg/h beyond the target  $UF_{NET}$  rate range in the assigned treatment group will not constitute a protocol deviation when the bedside team titrated the  $UF_{NET}$  rate as required to manage the patient hemodynamics (*i.e.*, when clinicians appropriately decreased rate or stopped  $UF_{NET}$  for MAP  $<65$  mm Hg or increased rate for MAP  $\geq 90$  mm Hg).

We will also calculate “%on target” value for each center for each of the monitored variables (# of dates on-target for a specific variable/# of opportunities to be on-target for that specific variable). Principle Investigators at each site will receive monthly reports of (1) % on-target for each of the specific variables in the most recent month; (2) % on-target for each of the variables since the beginning of a trial; and (3) a list of dates/times from the past month, the specific data that were entered for those dates/times, and determinations of on- or off-target.

Investigators will use these reports to identify aspects of protocol management that can be improved at their sites. The on-target performances of all ICUs will also be included, allowing investigators at each center to know how their ICU is performing related to other ICUs. On-target performances will be discussed during regular meetings of the Steering Committee.

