## F. TIME-EVENTS SCHEDULE

### F1. GENERAL DATA COLLECTION

Measurement/Event	Screening	Baseline/ Day 0@	1	2	3	4	5	6	7	8- 14	15- 21	22- 28
Serum Creatinine	X	X	X	X	X	X	X	X	X	X	X	X
Demographics, History and Physical		X										
AKI Cerner alerts	X	X										
Etiology of AKI		X										
APACHE II		X										
Weight*		X	X	X	X	X	X	X	X	X	X	X
Daily FB*		X	X	X	X	X	X	X	X	X	X	X
Restrictive UF NET		X	X	X	X	X	X	X	X	X	X	X
Liberal UF NET		X	X	X	X	X	X	X	X	X	X	X
Ventilator parameters ΦΨ*		X	X	X	X	X	X	X	X	X	X	X
CKRT parameters ΦΨ\$		X	X	X	X	X	X	X	X	X	X	X
ABG*		A	A	A	A	A	A	A	A	A	A	A
Fluids (intake/output)*		X	X	X	X	X	X	X	X	X	X	X
MAP*		X	X	X	X	X	X	X	X	X	X	X
CVP, CI, PPV, SVV, and other hemodynamic data*		A	A	A	A	A	A	A	A	A	A	A
Hypotensive & Hypertensive episodes \$%		X	X	X	X	X	X	X	X	X	X	X
Cardiac arrhythmias \$%		X	X	X	X	X	X	X	X	X	X	X
Use of rescue UF NET rates \$		X	X	X	X	X	X	X	X	X	X	X
Severe hypophosphatemia\$		X	X	X	X	X	X	X	X	X	X	X
Severe hypokalemia\$		X	X	X	X	X	X	X	X	X	X	X
Severe hypocalcemia		X	X	X	X	X	X	X	X	X	X	X
All lab data*		X	X	X	X	X	X	X	X	X	X	X
Vital signs and medications*		X	X	X	X	X	X	X	X	X	X	X
Inability to close surgical wounds		X	X	X	X	X	X	X	X	X	X	X
New organ dysfunction*		X	X	X	X	X	X	X	X	X	X	X
Secondary infections		X	X	X	X	X	X	X	X	X	X	X
SOFA score β*	X	X	X	X	X	X	X	X	X	X	X	X
Vital status		X	X	X	X	X	X	X	X	X	X	X

Measurement/Event	Screening	Baseline/ Day 0@	1	2	3	4	5	6	7	8- 14	15- 21	22- 28
KRT Status		X	X	X	X	X	X	X	X	X	X	X
IHD use			X	X	X	X	X	X	X	X	X	X

X= Required

A=When available

Ψ=Data gathered at times indicated or until 72 hours, whichever occurs first

β=Records clinically available creatinine, platelets, bilirubin, MAP, SBP, FiO2, fluid bolus and vasopressor use

ϕ=Measure during reference period (0600 -1000); other values may be obtained closest to 0800 on the specified calendar date

\* = collected only if the patient is still in the ICU before day 28 and if available in the electronic health records

\$\_= collected only if the patient is on CKRT upto 24 hours following discontinuation of CKRT

%=collected only if the patient is on IHD

@ =Data collected before initiation of study intervention

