### 4.2.2 PROTOCOL ADHERENCE

We have defined protocol deviation *a priori* as delivered UFNET rate that lies  $>0.5$  mL/kg/h outside of the target UFNET rate range in the assigned treatment group for greater than six consecutive hours during fluid removal *without* significant changes in MAP (*i.e.*, MAP  $< 65$  mmHg or  $\geq 90$  mmHg). As such, out of range UFNET rates  $>0.5$  mL/kg/h beyond the target UFNET rate range in the assigned treatment group will not constitute a protocol deviation when the bedside team titrated the UFNET rate as required to manage the patient hemodynamics (*i.e.*, when clinicians appropriately decreased rate or stopped fluid removal for hypotension; increased fluid removal rate for hypertension or for treatment of respiratory distress due to fluid overload and pulmonary edema).

We will report the following stratified by restrictive and liberal UFNET rate groups: i.) no. of occurrences of deviations for six consecutive hours divided by UFNET days (mean events per day); ii.) no. of days with UFNET out of range for at least six consecutive hours; iii.) no. of patients with at least one occurrence of UFNET rate out of range for six consecutive hours. The proportion of patients with protocol deviation will be compared using the Wald test for GLMM and adjusted for prespecified covariates.

As an exploratory analysis, we will also report the proportion of total hours of UFNET rate within, above, or below range for each patient weighted equally and proportionally to total hours of fluid removal.

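### The MAP exemption in the primary deviation definition has no direction while the sentence after it does, so wrong-way runs are scored two ways and coding the definition excuses them

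*Protocol*

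**What the plan says.** Protocol 5.8.1, item 2, defines a deviation as a delivered rate more than 0.5 mL/kg/h outside the assigned range "for greater than six consecutive hours during fluid removal *without* significant changes in MAP (*i.e.*, MAP <65 mmHg or" ≥90 mmHg). SAP 4.2.2 repeats the condition ("for greater than six consecutive hours during fluid removal *without* significant changes in MAP"), and Protocol 10.1 carries it too.

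In each place a second sentence follows, introduced as a consequence of the first. In 5.8.1 a run is not a deviation "when clinicians appropriately decreased rate or stopped fluid removal for hypotension; increased rate for hypertension or for treatment of respiratory distress" from fluid overload. SAP 4.2.2 agrees, excusing cases where clinicians "increased fluid removal rate for hypertension or for treatment of respiratory distress due to fluid overload and pulmonary edema". Protocol 10.1 also speaks of occasions "when clinicians appropriately decreased rate or stopped" removal, but ties the decrease to MAP <65 and the increase to MAP ≥90, and it omits respiratory distress.

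On data, Protocol 8.3.2 presents its list as the basis for assessing compliance and records the UFNET rate hourly. MAP is not in that list, nor in the daily reference list after it. Appendix F1 marks MAP in each day column, taken from the health record if available, with no within-day frequency.

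**The concern.** The second sentence reads as if it followed from the first, but it does not. The definition removes any run with MAP outside 65–89 mmHg. The explanation removes only runs in which the rate moved in the direction that the pressure would call for. A programmer working from the definition and one working from the explanation would produce different counts for a primary outcome.

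The runs in dispute are plain non-adherence: a liberal patient left below range although pressure is high, and a patient kept above range although pressure is low. The second also conflicts with the protocol's own text. Section 7.4.2.2 counts a new MAP <65 as hemodynamic instability, and section 11.4 says the protocol mandates a complete stop of fluid removal when instability develops. The definition would nevertheless not score more than six hours of above-range removal at that pressure as a deviation.

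**Working it through.** **Inputs.** Target ranges are 0.5–1.5 mL/kg/h (restrictive, Protocol 7.1) and 2.0–5.0 mL/kg/h (liberal, Protocol 7.2). The margin is 0.5 mL/kg/h, the duration more than six hours, and the MAP cut-offs 65 and 90 mmHg (Protocol 5.8.1 and 10.1, SAP 4.2.2). The documents state no expected deviation rate, so there is no figure of the plan's to reproduce.

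**Step 1: rates at which a run can become a deviation** (range limit ∓ margin).
- Restrictive, low side: 0.5 − 0.5 = 0. A rate below 0 is not fluid removal, so this deviation cannot occur during removal.
- Restrictive, high side: 1.5 + 0.5 = 2.0.
- Liberal, low side: 2.0 − 0.5 = 1.5.
- Liberal, high side: 5.0 + 0.5 = 5.5.

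**Step 2: score each combination.** The run exceeds six hours, with no respiratory or rescue indication. The explanation is read as the complete list of MAP exemptions, with the cut-offs in Protocol 10.1.

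| Rate | MAP (mmHg) | Definition | Explanation | Agree? |
|---|---|---|---|---|
| Below range | <65 | exempt | exempt | yes |
| Below range | 65–89 | deviation | deviation | yes |
| Below range | ≥90 | exempt | deviation | **no** |
| Above range | <65 | exempt | deviation | **no** |
| Above range | 65–89 | deviation | deviation | yes |
| Above range | ≥90 | exempt | exempt | yes |

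Four of six cells agree and two do not. By Step 1, the disputed runs are restrictive above 2.0 or liberal above 5.5 mL/kg/h with MAP <65, and liberal below 1.5 mL/kg/h with MAP ≥90. The low-side dispute arises only in the liberal arm.

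**Step 3: which coding the text favours.** The definition joins three conditions: out of range, longer than six hours, and no abnormal MAP. A wrong-way run fails the third, so it is not a deviation. The explanation lists circumstances that exempt a run; it never says that runs outside the list count. Taken literally, the definition prevails and both disputed cells are excused.

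**Step 4: whether other text settles it.**
- Respiratory distress excuses a high-side run in 5.8.1 and SAP 4.2.2, but not in 10.1.
- Protocol 7.4.6 says rescue rates are not a protocol violation, and Table 5 lists criteria beyond respiratory distress.
- Protocol 7.4.2.2 and SAP 5.2.2.1 define instability or hypotension by systolic pressure, vasopressor and fluid-bolus criteria as well as MAP <65.
- SAP 5.2.2.2 defines intradialytic hypertension with MAP ≥80 for more than one hour, against ≥90 in the deviation rule. Recorded hypertensive episodes therefore cannot stand in for the exemption.
- The three reporting items in SAP 4.2.2 do not restate the MAP condition.
- No section says when, or for how many hours of the run, MAP must be abnormal.

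**The case against.** The strongest reply is that the plan does state direction. The explanatory sentence appears in all three places, 10.1 attaches the MAP cut-offs to it, and a sensible analyst would read the two sentences together. That stands as evidence of intent, and a reader should not infer that the sponsor ignored direction or meant to excuse wrong-way runs. It does not cure the definition, which still exempts them as written, and the word for appropriate action leaves the exemption to judgement in an unblinded trial.

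A reader might also infer that MAP is scheduled once a day, so that most runs could not be classified. The documents do not support this. The F1 footnote allowing that "other values may be obtained closest to 0800 on the specified calendar date" is attached to the ventilator and CKRT rows, not to MAP. The UFNET rows also carry one mark per day column, yet that rate is recorded hourly. Blood pressure is monitored continuously (Protocol section 4, item 11, and section 11.4), hypotensive and hypertensive episodes are collected, and reasons for non-adherence are recorded. What remains is narrower: no section says that hourly MAP will be captured for this outcome, and a reason code records what staff attributed the run to, not the pressure.

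Two further points stand. SAP 4.2.2 reports hours within, above and below range with no stated MAP exemption, so wrong-way hours are not lost, though that analysis is exploratory and does not show MAP. And a rule that exempted low-side runs only for MAP <65, and high-side runs only for MAP ≥90 or respiratory distress, would collide with the rescue provision and the wider instability definition. The fix has to avoid that.

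**Conclusion.** The point holds as a conflict between two sentences that define a primary outcome. They score two of six direction-by-MAP combinations differently, and the definition, coded as written, excuses wrong-way runs in both. The bias in the adherence figure is towards fewer deviations.

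Its size is unknown. It depends on how often out-of-range runs coincide with MAP abnormal in the opposite direction, and the documents give neither run lengths nor a MAP distribution. If clinicians lower or stop removal when pressure falls, as the protocol directs, few runs may be affected. The effect on the between-group comparison cannot be derived either.

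The two-of-six count assumes that the explanatory sentence is the complete list of MAP exemptions and that no respiratory or rescue indication applies. The change should be made because the outcome is primary and the direction is already in the sponsor's text. On data capture, the finding is only that the frequency and timing of MAP are unstated.

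**What to change.** Merge the two sentences into one programmable rule and use it unchanged in Protocol 5.8.1, Protocol 10.1 and SAP 4.2.2:

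1. Match the exemption to the side of the range, using the direction already written: a low-side run can be exempt for low pressure and a high-side run for high pressure. State that MAP abnormal in the opposite direction does not by itself exempt a run.
2. Reconcile the exemption list with the existing provisions: respiratory distress (absent from 10.1), rescue use (7.4.6 and Table 5), the wider hypotension and instability definitions (7.4.2.2 and SAP 5.2.2.1), and the MAP ≥80 and ≥90 values. The sponsor should settle which definitions apply; no new clinical rule is needed.
3. State how MAP is matched in time to the run, including how many of its hours must be abnormal.
4. Name hourly MAP from the health record beside the hourly UFNET rate in 8.3.2, and give its frequency in Appendix F1.
5. Have the SAP 4.2.2 reporting items refer to the merged rule.

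The cost is a short edit in three places, consequential edits to 8.3.2, F1 and the reporting items, and a modest extra data extract. The adherence figure may come out less favourable.
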